#### 9.4.3 Handling of missing values/censoring/discontinuations

The method of handling missing data for efficacy endpoints will be described for each set of endpoints. For the primary analysis, missing data will not be imputed, but various sensitivity analyses under missing at random and missing not at random assumptions will be performed. Missing data will not be imputed for safety endpoints. Details of the missing data handling will be specified in the statistical analysis plan (SAP).

#### 9.4.4 Sensitivity analyses

Multiple imputation (MI) techniques applying missing at random (MAR) and missing not at random (MNAR) approaches will be used to assess the impact of missing values on the interpretation of the results during the DBTP. In addition, the baseline observations carried forward (BOCF) method will also be used.

## 9.5 Analysis of secondary variables

#### 9.5.1 Efficacy variables

The secondary efficacy variables (all during the DBTP) are:

- Proportion of patients who achieve at least a 50% reduction from baseline in monthly migraine days in the last month of DBTP (Month 3).
- Change from baseline in monthly acute migraine-specific treatment days in Month 3 of the DBTP
- Change from baseline in headache impact scores as measured by the HIT-6 in Month 3 of the DBTP

The above continuous endpoints (ie, change from baseline) will be analyzed using a linear mixed effects model similar to the primary endpoint. The dichotomous endpoints will be analyzed by Cochran-Mantel-Haenszel (CMH) test with patients who are missing monthly migraine day data at Month 3 of the DBTP imputed as non-responders. Nominal 95% confidence intervals and p-values will be reported.

A hierarchical gate-keeping procedure and the Hochberg method will be used to maintain the overall 2-sided study-wise type I error rate at 0.05 for the primary endpoint and secondary efficacy endpoints. The primary endpoint, the change from baseline in monthly migraine days to the last 4 weeks of the 12-week double-blind treatment period, will be initially tested at a 2-sided significance level of 0.025 for each of the AMG 334 treatment group (140 mg and 70 mg) compared to the placebo group, respectively. If the primary endpoint and all secondary endpoints are statistically significant for an AMG 334 treatment group, the corresponding significance level will be carried over to the primary endpoint for the other AMG 334 treatment group, and the primary endpoint will be re-compared to the placebo group at a 2-sided significance level of 0.05 (full alpha). If the primary endpoint of one dose group is statistically significant but not all the secondary endpoints, only half of the initial alpha of the dose (0.0125) can be transferred to the primary endpoint of the other dose. The testing sequence can be found in the figure below.

#### Figure 9-1 Hierarchical Testing Procedure

#### 9.5.2 Safety variables

Safety variables are:

- Adverse events
- Clinical laboratory values and vital signs
- Anti-AMG 334 antibodies

As safety analyses, patient incidence of treatment-emergent adverse events will be tabulated by system organ class and preferred term by treatment group. Change from baseline for clinical laboratory values and vital signs will be summarized by visit and by treatment group.

The incidence and percentage of subjects who develop anti-AMG 334 antibodies (binding and if positive, neutralizing) at any time will be tabulated by treatment group.

All safety analyses will be performed for the Double-Blind Treatment Period and Safety Follow-up Period separately.

#### 9.5.3 Resource utilization

Data relating to resource utilization will be used for the purpose of economic evaluation which will be carried out and reported as a separate activity.

#### 9.7 Interim analyses

To account for potential larger than expected variabiality during the DBTP of the trial, a blinded interim assessment is planned after about 50% of subjects finish their DBTP or early withdraw. Only the standard deviation of the primary variable, change from baseline in monthly migraine days in month 3, based on pooled (blinded) data from all subjects who had the opportunity to complete the week 12 assessment in the trial, will be estimated. The sample size will be increased appropriately, up to an additional 200 subjects, only if the standard deviation is larger than 5.

The type I error of the primary analysis will be maintained, as the treatment assignment will remain blinded and there is no intention to stop the study early due to efficacy.

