# 3 Investigational plan

### 3.1 Study design

This study uses a single-cohort, 3-treatment arm, randomized (2:3:3 [140 mg: 70 mg: placebo]), double-blind study design in adult patients with episodic migraine. A screening period of 2 weeks will be used to assess initial eligibility, followed by a 4-week baseline period (the maximum duration for the baseline period is 35 days), during which diary compliance and headache frequency will be assessed for a final eligibility assessment prior to randomization and dosing. After randomization/Day 1, visits will occur at four week intervals until Week 12, which is the End of Treatment visit, Last Patient Last Treatment (LPLT). The final visit, Last Patient Last Visit (LPLV), a Safety Follow-Up visit, will occur 12 weeks later, at Week 24.

A blinded interim analysis after approximately 50% patients have completed the DBTP will be conducted to re-estimate the sample size by providing information on the variance for this trial relative to the planning assumptions to account for potential higher variability in Asian countries/new sites.

End of Trial will occur when the last patient completes their last visit (LPLV) of the study.

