### 3.5 **Purpose and timing of interim analyses/design adaptations**

A blinded interim assessment is planned after about 50% of subjects have completed their DBTP, including early withdrawals, to provide additional information on the variance of the primary endpoint in this trial. The purpose of this blinded interim analysis is to account for potential higher variability in new countries and sites and possibly modify the initially planned sample size as outlined in Section 9.7.

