Three additional Phase 2/3 studies, including 2 studies in EM, have been completed with AMG 334, which have established 70 mg and 140 mg as being effective and safe in patients with EM or CM, with a favorable benefit/risk profile. Positive treatment effects in general were observed in a robust way across typical migraine endpoints such as change in mean monthly migraine days, > 50% (and higher) responder rates, change in migraine-specific medication use and functional improvement by established PRO scales. Results were in general highly statistically significant and clinically meaningful. As described in Section 3.3, in episodic migraine a dose-dependent increase in efficacy has been observed for the 140 mg dose. Retention rates observed in clinical trials were very high (~95% with active treatment after 3 months and ~90% after 6 months with only minimal discontinuations attributed to

adverse events). This feature is important, as discontinuation rates are high for current migraine prophylaxis treatments, with the main drivers of discontinuation being either lack of efficacy or tolerability issues (Blumenfeld et al 2013). As such, there is a high unmet need for a therapy that is well-tolerated, has sustained response rates and excellent compliance.

Overall, given the characteristics of AMG 334 and the large experience in clinical trials, the overall benefit-risk assessment is supportive.

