#### 9.8 Sample size calculation

A treatment difference of -1.79 days for change from baseline in monthly migraine days in Month 3 between AMG 334 140mg and placebo was observed in study 20120296 (STRIVE). A treatment difference of -1.16 days for change from baseline in monthly migraine days in Month 3 between AMG 334 70mg and placebo was observed based on pooled analysis on the combined data from studies 20120296, 20120297, and 20120178.

Assuming a treatment effect similar to the effect observed in previous studies with AMG 334 in episodic migraine, the treatment difference in terms of change from baseline on monthly migraine days during week 9-12 (primary variable) for erenumab 140mg vs. placebo and 70mg vs. placebo is assumed at -1.5 days and -1.1 days, respectively. The common standard deviation of the primary variable is assumed at 4. Given a 2:3:3 randomization ratio among erenumab 140mg, 70mg, and placebo, a total of 880 subjects (including 10% drop out rate) would enable both doses to achieve higher than 90% power under overall 0.05 full alpha level to detect the designed treatment difference. In addition, the sample size will also ensure the trial to have adequate power to detect treatment difference under initial 2-sided 0.025 alpha level assigned to each dose (equally split between the erenumab two doses).

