1.1 Study design

This study uses a single-cohort, 3-treatment arm, randomized (2:3:3 [140 mg: 70 mg: placebo]), double-blind study design in adult patients with episodic migraine.

The following periods are included in the study design:

- Screening period of 2 weeks: to assess initial eligibility,
- Baseline period of 4 weeks: All patients successfully completing the Screening period are invited to participate. Final eligibility prior to randomization and dosing will be assessed based on headache frequency and diary compliance during this period,
- Double-blind treatment period (12 weeks): All patients successfully completing the Baseline period are invited to participate. Eligible patients will be randomized to one of three treatment arms. After randomization/Day 1, visits will occur at four week intervals until Week 12, which is the End of Treatment visit.
- Safety follow-up period: the final visit, a Safety Follow-Up visit, will occur 12 weeks later, at Week 24.

A blinded interim analysis after approximately 50% patients have completed the DBTP (including early withdrawals) will be conducted to re-estimate the sample size by providing information on the variance for this trial relative to the planning assumptions to account for potential higher variability in Asian countries/new sites.

End of Trial (Last Patient Last Visit, LPLV) will occur when all patients have completed their last visit.

Approximatively 880 patients will be randomized (330 in placebo, 330 in AMG334 70mg and 220 in AMG334 140mg), stratified by prior prophylactic migraine medication treatment failure (prior prophylactic migraine treatment failure, due to efficacy or tolerability, vs no prior prophylactic migraine treatment failure).

The primary analysis and all other efficacy and safety analyses will be conducted at the end of study after the database lock; i.e., at the time point when all patients have completed their last visit.

Figure 1-1 Study Design Schematic

| Screen | Baseline | Double-Blind Treatment | Follow-Up |
|---------|----------|------------------------|-----------|
| 2 weeks | 4 weeks | 12 weeks | 12 weeks |

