2.13 Interim analysis

To account for potential larger than expected variability during the DBTP of the trial, a blinded interim assessment is planned after about 50% of subjects finish their DBTP or early withdraw. Only the standard deviation of the primary variable, change from baseline in monthly migraine days in month 3, based on pooled (blinded) data from all subjects who had the opportunity to complete the week 12 assessment in the trial, will be estimated. The sample size will be increased appropriately, up to an additional 200 subjects, only if the standard deviation is larger than 5.

The type I error of the primary analysis will be maintained, as the treatment assignment will remain blinded and there is no intention to stop the study early due to efficacy.

3 Sample size calculation

A treatment difference of -1.79 days for change from baseline in monthly migraine days in Month 3 between AMG 334 140mg and placebo was observed in study 20120296 (STRIVE).

A treatment difference of -1.16 days for change from baseline in monthly migraine days in Month 3 between AMG 334 70mg and placebo was observed based on pooled analysis on the combined data from studies 20120296, 20120297, and 20120178.

Assuming a treatment effect similar to the effect observed in previous studies with AMG 334 in episodic migraine, the treatment difference in terms of change from baseline on monthly migraine days during week 9-12 (primary variable) for erenumab 140mg vs. placebo and 70mg vs. placebo is assumed at -1.5 days and -1.1 days, respectively. The common standard deviation of the primary variable is assumed at 4. Given a 2:3:3 randomization ratio among erenumab 140mg, 70mg, and placebo, a total of 880 subjects (including 10% drop out rate) would enable

| Novartis | For business use only | Page 48 |
|-----------------|-----------------------|--------------|
| SAP Amendment 1 | | CAMG334A2302 |

both doses to achieve higher than 90% power under overall 0.05 full alpha level to detect the designed treatment difference. In addition, the sample size will also ensure the trial to have adequate power to detect treatment difference under initial 2-sided 0.025 alpha level assigned to each dose (equally split between the erenumab two doses).

4 Change to protocol specified analyses

The following analyses will be performed and are not planned in the protocol

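### Must the re-estimation rule (SD above 5, at most 200 more patients) change because it does not hold 90% power for 70 mg?

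*Protocol*

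**What the plan says.** The look has a declared purpose. Protocol 3.1 plans it "to re-estimate the sample size by providing information on the variance for this trial relative to the planning assumptions", and Protocol 3.5 says it is there to "account for potential higher variability in new countries and sites and possibly modify the initially planned sample size as outlined in Section 9.7". Protocol 9.7 then fixes the rule, repeated in SAP 2.1 and SAP 2.13: "The sample size will be increased appropriately, up to an additional 200 subjects, only if the standard deviation is larger than 5". The text names no dose, alpha level, power target or formula for the size of the increase.

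The only numeric power statement is in Protocol 9.8, repeated in SAP section 3. The assumed differences from placebo are 1.5 days (140 mg) and 1.1 days (70 mg), and "The common standard deviation of the primary variable is assumed at 4". With 2:3:3 allocation and 10% dropout, 880 patients "would enable both doses to achieve higher than 90% power under overall 0.05 full alpha level to detect the designed treatment difference". For the initial 0.025 level per dose, 9.8 promises only adequate power, without a figure. SAP 1.1 gives the arm sizes: "Approximatively 880 patients will be randomized (330 in placebo, 330 in AMG334 70mg and 220 in AMG334 140mg").

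**The concern.** The look exists because new countries and sites may be more variable than the planning SD of 4, yet the rule stays silent until the SD is 25% above that value. Between about 4.14 and 5, power for 70 mg slides below 90% and nobody is added. Above 5, the permitted 200 patients are too few to bring it back: 90% at SD 5 needs about 880 × (5/4.135)² ≈ 1,287 patients. So, on the planning inputs, at no SD does the rule both add patients and restore 90% for 70 mg. That dose is one of two primary comparisons and 9.8 names both. At stake is a 70 mg result that misses significance because the trial was too small for the variability it met.

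**Working it through.** **Inputs.** Differences 1.1 and 1.5 days, SD 4, 10% dropout, two-sided 0.05 (Protocol 9.8); 330/330/220 randomized (SAP 1.1); trigger 5 and cap +200 (Protocol 9.7).

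Evaluable patients:
- N = 880: 330 × 0.9 = 297 for 70 mg and for placebo; 220 × 0.9 = 198 for 140 mg.
- N = 1,080: 405 × 0.9 = 364.5 and 270 × 0.9 = 243.

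**Formula** (normal approximation): power = Φ( Δ / [SD × √(1/n₁ + 1/n₂)] − 1.96 ).

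**1. The plan's own figure (N = 880, SD 4).**
- 70 mg: 1.1 / (4 × 0.08206) − 1.96 = 1.39, power 91.8%.
- 140 mg: 1.5 / (4 × 0.09175) − 1.96 = 2.13, power 98.3%.

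The claim of more than 90% reproduces.

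**2. Largest SD that keeps 90%:** Δ / [(1.960 + 1.282) × √(1/n₁ + 1/n₂)].
- 70 mg: 4.135 with 880; 4.581 with 1,080.
- 140 mg: 5.044 with 880; 5.588 with 1,080.

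**3. Power at two-sided 0.05.**

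| SD | 70 mg, 880 | 70 mg, 1,080 | 140 mg, 880 | 140 mg, 1,080 |
|---|---|---|---|---|
| 4.0 | 91.8% | 96.0% | 98.3% | 99.5% |
| 4.5 | 84.6% | 91.0% | 95.3% | 98.1% |
| 5.0 | 76.5% | 84.4% | 90.5% | 95.2% |

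At the initial 0.025 level with 880 and SD 5, 70 mg has 67.0% and 140 mg 84.8%. In simulation, at least one dose succeeds at that level in 90.8% of trials.

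**4. Pooled scale.** Section 9.7 measures a blinded pooled SD, which includes the differences between arms. At the planned effects the between-arm variance is 0.396. The 70 mg limits become √(4.135² + 0.396) = 4.18 and √(4.581² + 0.396) = 4.62. A pooled SD of 5 means √(25 − 0.396) = 4.96 within arm.

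**5. How firm are the 70 mg limits?** They use the raw SD and discard all dropouts, as 9.8 does. The primary model adjusts for baseline and stratum.
- Covariates would have to explain 1 − (4.581/5)² = 16% of the variance for 1,080 to reach SD 5, and 1 − (4.135/5)² = 32% for 880. Neither document gives such a share.
- With 5% dropout (Protocol 3.6: "Retention rates observed in clinical trials were very high (~95% with active treatment after 3 months") and the observed 1.16 days from 9.8 in place of 1.1, the limits are 4.48 and 4.96. The latter is about 5.00 on the pooled scale.

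**6. What a lower trigger would buy.** Take a rule that acts when the pooled SD exceeds 4.14, with N = 880 × (SD/4.135)² and the same cap. It was simulated with normal data and 396 evaluable patients at the look; the present rule was credited with the full +200 whenever it fires.
- True SD 4.5: the present trigger fires in 0.2% of trials. 70 mg power is 84.6% now and 89.9% under the lower trigger, for about 162 more patients on average.
- True SD 4.8: the present trigger fires in 17%; power is 81.0% against 87.1%.
- True SD 4.0, as planned: the lower trigger fires in about 25% of trials although 880 already gives 91.8%. It costs about 11 patients on average.

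**The case for a change.** The strongest case for a change is that the rule does little for its declared purpose. If the true SD is 4.5, the 200 patients already budgeted would bring 70 mg to 91.0%, but the trigger almost never releases them. The word *appropriately* does not let anyone derive the new N. Moving one threshold would leave the maximum of 1,080, the blinding and the type I error as they are.

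The arithmetic stands, and so does the gap in documentation: the basis of the 5 and the 200 is not written down. The step from there to a required change does not stand.
- Power is promised at SD 4 only, and nothing in 3.1, 3.5 or 9.7 undertakes to hold it at other values.
- A trigger of 5 is where 140 mg is about to lose 90%. Protocol 1.1 regards 140 mg as having the best benefit-risk ratio, so setting the rule on that dose is coherent, although the documents do not say that this was the intention.
- Baseline adjustment could recover part of the 70 mg loss.
- The lower trigger has its own fault: 4.14 is a within-arm limit applied to a pooled SD, for which the matching value is 4.18. Correcting that would still leave a rule that enrols many more patients to raise one dose by about five percentage points.

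**Conclusion.** The plan can stand. On the planning inputs the rule does not guard 90% for 70 mg above a within-arm SD of 4.14 with 880 patients, or 4.58 with 1,080. At the trigger, 70 mg has 76.5% with 880 and 84.4% with the full increase. That is a fair trade-off rather than an error: the stated power is correct where it is stated, 140 mg keeps 90.5% with 880 at SD 5, and validity is not touched. The limits assume the raw SD, 10% dropout and 1.1 days, and they move upward under milder dropout, a slightly larger effect or useful covariates.

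What *appropriately* leaves open is a blinded decision bounded by the cap, and a statistician can settle it from the 9.8 inputs. Timing points the same way. SAP Amendment 1 is dated 26-Feb-2020 and already draws on blinded review and observed data, so the half-way look has very probably passed, although the documents do not report its result. A new trigger would then have no use, and recording the interim SD and the decision would not alter any analysis.

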#### 9.8 Sample size calculation

A treatment difference of -1.79 days for change from baseline in monthly migraine days in Month 3 between AMG 334 140mg and placebo was observed in study 20120296 (STRIVE). A treatment difference of -1.16 days for change from baseline in monthly migraine days in Month 3 between AMG 334 70mg and placebo was observed based on pooled analysis on the combined data from studies 20120296, 20120297, and 20120178.

Assuming a treatment effect similar to the effect observed in previous studies with AMG 334 in episodic migraine, the treatment difference in terms of change from baseline on monthly migraine days during week 9-12 (primary variable) for erenumab 140mg vs. placebo and 70mg vs. placebo is assumed at -1.5 days and -1.1 days, respectively. The common standard deviation of the primary variable is assumed at 4. Given a 2:3:3 randomization ratio among erenumab 140mg, 70mg, and placebo, a total of 880 subjects (including 10% drop out rate) would enable both doses to achieve higher than 90% power under overall 0.05 full alpha level to detect the designed treatment difference. In addition, the sample size will also ensure the trial to have adequate power to detect treatment difference under initial 2-sided 0.025 alpha level assigned to each dose (equally split between the erenumab two doses).

# **10** Ethical considerations

#### **10.1** Regulatory and ethical compliance

This clinical study was designed and shall be implemented, executed and reported in accordance with the ICH Harmonized Tripartite Guidelines for Good Clinical Practice, with applicable local regulations (including European Directive 2001/20/EC, US CFR 21, and Japanese Ministry of Health, Labor, and Welfare), and with the ethical principles laid down in the Declaration of Helsinki.

#### **10.2** Informed consent procedures

Eligible patients/subjects may only be included in the study after providing (witnessed, where required by law or regulation), IRB/IEC-approved informed consent, or, if applicable after such consent has been provided by a legally acceptable representative(s) of the patient. Informed consent must be obtained before conducting any study-specific procedures (eg all of the procedures described in the protocol). The process of obtaining informed consent must be documented in the patient.

For trials using an Electronic Informed Consent system where a date/timestamp is automatically generated, the system-generated date/timestamp is sufficient; additional input of the date at the time of consent is not required by the patient.

Novartis will provide to investigators in a separate document a proposed informed consent form that complies with the ICH GCP guideline and regulatory requirements and is considered appropriate for this study. Any changes to the proposed consent form suggested by the investigator must be agreed to by Novartis before submission to the IRB/IEC, and a copy of the approved version must be provided to the Novartis monitor after IRB/IEC approval.

Women of child bearing potential must be informed that taking the study treatment may involve unknown risks to the fetus if pregnancy were to occur during the study and agree that in order to participate in the study they must adhere to the contraception requirement for the duration of the study. If there is any question that the patient will not reliably comply, they must not be entered in the study.

The study includes an optional DNA component which requires a separate signature if the patient agrees to participate If optional DNA collection for the study is approved by the site IRB/IEC board. It is required as part of this protocol that the Investigator presents this option to the patient. The process for obtaining consent should be exactly the same as described above for the main informed consent.

Declining to participate in these DNA assessments will in no way affect the patient's ability to participate in the main research study.

